#### **Evaluation of severity and duration of reported cases of influenza and ARI, complications:**

When recording a case of influenza or ARI, a study doctor will perform an evaluation of its duration, making additional telephone calls, where necessary, and determine its severity. In this study, a case with at least one of the complications listed below will be considered severe:

- the necessity of hospitalization,
- influenza-associated pneumonia,
- influenza-associated cardiovascular disorder,
- death.

---

Strictly confidential. Proprietary Information.  
[name]

## 7. SAFETY EVALUATION

### 7.1. Review of the safety parameters

Safety parameters are listed in Section 3.1.

### 7.2. Methods and terms of evaluation, recording, and analysis of safety parameters

Evaluation of local and systemic reactions, as well as AEs, will be performed from the moment of immunization and within 6 months of follow-up. Recording of safety parameters will include the following procedures:

- clinical interview of a study subject;
- recording of thermometry results and complaints of a study subject related to his/her medical condition in a volunteer's diary;
- physical examination (including neurological status);
- vital signs;
- laboratory investigations
  - complete blood count and blood chemistry;
  - urinalysis;
  - evaluation of immunological parameters: serum immunoglobulin content (ELISA: IgE);
- quantitative assessment and nature (severity and duration) of local and systemic reactions to vaccine administration (reactogenicity);
- recording of AEs and SAEs associated with the study vaccines;
- recording of immediate type AEs, emerging within one hour after immunization;
- evaluation of incidence and nature of intercurrent disorders.

#### **Clinical interview of a study subject:**

During Visits 1–11 (post-immunization) the investigator shall perform a clinical interview of a study subject to collect information on the study subject's medical condition. At that, the investigator shall ask a study subject the following routine question at every visit:

***"Have there been any changes in your condition since our last conversation / meeting?"***

Clinically significant symptoms will be recorded by the investigator in the source medical documentation and CRF as AEs.

#### **Recording of thermometry results and complaints of a study subject in a volunteer's self-observation diary:**

A study subject will record axillary temperature in a self-observation diary every day, in the morning and in the evening, starting from Visit 1 after immunization and till Visit 7 (further measurements — depending on condition). He/she will also record concomitant therapy and complaints related to his/her medical condition during the day (if any); to do so, a subject will be offered to answer the

Strictly confidential. Proprietary Information.  
[name]

following question in the volunteer's diary in writing:

***"Have there been any changes in your condition since yesterday?"***

Clinically significant symptoms will be recorded by the investigator in the CRF as AEs.

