## **5.3. Methods of control of compliance with procedures and subjects**

For the whole post-immunization follow-up period, the study subjects had to log in their volunteer's diaries information on the body temperature, any adverse events, and treatment with any medicinal drugs. At Visits 2–8, the investigator reviews the volunteer's diary and assesses the incidence and severity of adverse reactions, as well as the volunteer's compliance with the rules of concomitant therapy.

Additionally, the investigator assesses the regularity of the subject's visits to the trial site. The investigator can withdraw the subject from the study in case of subject's non-compliance with the requirements to concomitant therapy or if the study subject was not able to comply with the medical recommendations, in the investigator's opinion.

Strictly confidential. Proprietary Information.  
[name]

Study protocol does not provide for self-administration of the study products, the single dose immunization is performed at the trial site. The trial site personnel has to ensure that all the procedures related to the study product accountability are complied with (see Section 3.7).

As some of the study procedures (e.g., recording of AEs, blood sample collection, urine sample collection, vital signs measurement, physical examination, neurological examination, etc.) are performed by the investigator or another authorized personnel of the trial site at the study Visits, no methods of compliance control for such procedures are required.

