**Assessment of local and systemic reactions to vaccine administration (reactogenicity)**

For assessment of local and systemic reactions to vaccine administration, the results of daily examinations are recorded in a Case Report Form and an Outpatient Medical Record for each subject. Particular attention is paid to symptoms corresponding to clinical manifestations of influenza, allergic and neurological reactions. A local reaction is evaluated by the diameter of a hyperaemic skin area at the injection site, skin tenderness and oedema, and enlargement of regional lymph nodes.

The assessment is performed before immunization, 2 hours after immunization, then once a day for 5 post-immunization days; thermometry is mandatory. Subjects who responded to the vaccination are monitored until these reactions pass off completely. In case of development of any unusual reactions the subject will be examined by an appropriate specialist. The following parameters are used for evaluation of tolerability of the study drugs.

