#### *Safety analysis*

The safety analysis will be conducted by descriptive methods in the safety population. Adverse events will be coded using MedDRA. The number (percentage) of participants with AEs and the number of AEs will be presented in tables by system organ class and preferred term, as well as by the study therapy and severity.

---

Strictly confidential. Proprietary Information.  
[name]

With that, within a system organ class and preferred term, each subject will be considered once with regard to study therapy and maximum severity. The number (percentage) of volunteers with local and general reactions to vaccination will be presented taking into account severity and duration.

Laboratory findings and their changes after vaccination compared to the baseline and “shift tables” relative to normal values will be tabulated by therapeutic groups and by assessment points.

The results of the assessment of vital functions will be tabulated by therapeutic groups for each assessment point together with changes from the last available measurement prior to vaccination.

The results of physical examination will be presented descriptively by therapeutic groups and by assessment points.

Immunological parameters evaluation results: serum immunoglobulin content (ELISA: IgE) and their changes after vaccination compared to baseline values will be tabulated by therapeutic groups.

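### The diary is meant to record each day's complaints but asks only about change since yesterday, and the scripted visit question also asks only about change, so some short or continuing symptoms may go unrecorded

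*Combined protocol and SAP*

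**What the plan says.** Section 7.2 of the protocol (self-observation diary) gives the diary two tasks. Temperature is taken "every day, in the morning and in the evening, starting from Visit 1 after immunization and till Visit 7". The subject also enters "concomitant therapy and complaints related to his/her medical condition during the day (if any", and does this by answering one written question: "Have there been any changes in your condition since yesterday" No symptom list, size field or start and stop field is described for the diary. Section 5.3 describes the content a little more widely, to include any adverse event, and says that at visits "the investigator reviews the volunteer's diary and assesses the incidence and severity of adverse reactions".

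The clinical interview in Section 7.2 scripts one question for every visit. It asks whether the subject's condition has changed since the last contact.

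The reactogenicity part of Section 7.2 takes its data mainly from examinations: "The assessment is performed before immunization, 2 hours after immunization, then once a day for 5 post-immunization days". Six local and 14 systemic reactions are listed as the parameters, and subjects who react are followed until the reaction has gone. Section 7.3.1 asks for onset and resolution times of each adverse event, to the minute where possible. In the analysis (Section 8.1, safety), "The number (percentage) of volunteers with local and general reactions to vaccination will be presented taking into account severity and duration".

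**The concern.** The diary's stated purpose and its question do not match. A complaint that is the same as yesterday belongs in the diary by its purpose, but is not a change. The visit question has the same form, so in neither channel does a scripted question ask about a reaction by name.

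This matters most for symptoms that only the subject can report. Most of the 14 systemic items are of that kind, such as headache, malaise, nausea, and sleep or appetite disturbance. So are pain and itch among the local items. In the Phase I study summarised in Section 1.2, injection-site pain was the most common local reaction. Headache was the most common general reaction on the quadrivalent vaccine (13.8 %, against 3.6 % on the trivalent). Comparative reactogenicity is a stated purpose of the trial, and both the frequency and the duration of reactions will be tabulated.

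**Working it through.** The plan gives no figure to reproduce. The check sets the sections side by side and works out the gaps in the schedule.

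**1. What a truthful answer to the diary question records**

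| Situation today | A complaint today? | A change since yesterday? |
|---|---|---|
| Symptom has started | Yes | Yes |
| Symptom continues unchanged | Yes | No |
| Symptom has ended | Not necessarily | Yes |
| Symptom came and went between two answers | Yes | Depends on how the question is read |

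The second row is where purpose and question part. The fourth row is uncertain: a subject who compares how they feel now with how they felt yesterday may answer no.

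**2. What other channels cover**

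- Days 1–5: a daily examination against the named local and systemic lists. An unchanged reaction that lasts through consecutive visits can be picked up there.
- Known reactors: followed until resolution (Section 7.2).
- Symptoms entered as adverse events: onset and resolution times recorded (Section 7.3.1).
- Fever: measured twice daily in the diary until Visit 7, whatever the answer to the question.

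**3. Gaps between scheduled checks (Section 3.2 and Table 2)**

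- From the 2-hour check to Visit 2: 24 − 2 = about 22 hours, assuming that Visit 2 falls 24 hours after vaccination.
- Between Visits 2 and 6: about 24 hours each.
- From Visit 6 (Day 5) to Visit 7 (Day 22 ± 1): 21 − 5 = 16 days to 23 − 5 = 18 days.

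Section 1.3 says that the common reactions usually pass in 1–2 days, so onset or end will often fall between two daily checks.

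**4. What is left exposed**

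- Short non-temperature symptoms between daily checks.
- The precision of start and end times, since the diary is the only record made at the time between visits.
- The days after Visit 6 and before Visit 7. In that window the diary question is the only scheduled symptom prompt, apart from follow-up of reactors already recognised. Section 7.2 gives no schedule or method for that follow-up. At Visit 7 the subject is asked about change and about acute respiratory symptoms, looking back over 16–18 days.

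**5. Size**

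To size the loss one would need the share of reactions captured with and without a named prompt. The documents give neither, so no figure can be derived.

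**The case against.** The case against is substantial. The diary is not the main source for reactogenicity, and the persisting reaction that the question handles worst is the one that daily examinations catch best. Onset and resolution are themselves changes, so a careful subject who reports both supplies a duration. The surrounding text is wider than the question: Section 7.2 speaks of the day's complaints and Section 5.3 of any adverse event. Subjects are instructed at the site and make their first entries there. Neither the diary form nor those instructions are reproduced, so how subjects would actually answer is inference. The safety analysis is descriptive, with no reactogenicity hypothesis or margin, and the prompt is the same in every blinded arm.

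Most of this stands and sets the limits of the point. It does not remove the mismatch between purpose and question. It also does not help with a subjective symptom that was brief or not thought worth mentioning, because an examination cannot find it unless the subject is asked or volunteers it. The lists in Section 7.2 are evaluation parameters; the protocol does not say that they are read out to the subject.

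A reader might infer that a reaction lasting several days keeps only its first day in the data. That would require duration to be the count of days answered yes and the diary to be the only source. The documents say neither.

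**Conclusion.** The point holds as a weakness in how symptoms are elicited for a reported safety parameter. An unchanged continuing symptom may truthfully be answered no, and brief subjective symptoms between checks may go unmentioned. On Days 1–5 the examinations and the other safeguards contain most of the effect. The residual exposure is the three items in step 4 of the working.

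The expected effect is lower absolute rates and less precise durations in all arms. Its size cannot be calculated. This rests on two assumptions: that the diary page carries no more than Section 7.2 describes, and that the site instructions do not already tell subjects to enter continuing complaints.

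A reader might also infer a bias between vaccines, or a calculable shrinkage of the Phase I difference in systemic reactions. The documents do not support either. The prompt is common to all arms. No capture rate is given. The Phase I rates include temperature rises, which do not depend on this question, and the protocol does not say how Phase I symptoms were elicited. The immunogenicity endpoints are untouched.

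**What to change.** - From the evening of Day 0 to Day 5, and until any reaction resolves, use a daily diary checklist of the self-reportable reactions already listed in Section 7.2: present today yes or no, with start and stop.
- For later days up to Visit 7, ask: *Did you have any complaints today, new or continuing?*
- Reword the scripted visit question in the same way, so that it covers new and continuing complaints since the last contact.
- Add one sentence to Section 7.2: a reaction-day counts if the reaction is present in either the diary or the examination, and the higher grade is used.

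The cost is a reprinted diary page, one added CRF page and that sentence. No visit, treatment or sample size changes. The downside is slightly more diary entry and somewhat higher reported rates of mild reactions in all arms. The change has to be made before vaccination starts, because symptoms not recorded at the time cannot be reliably recovered later.

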**Physical examination (including neurological status):**

The investigator shall perform complete physical examination of a study subject during Visits 0, 1, 2, 3, 4, 5, 6, and 7. Apart from that, neurological examination (recording of neurological status) will be performed by a neurologist during Visits 1 and 3. Height and weight measurements of a study subject will only be taken during Screening visit. Clinically significant deviations identified during physical and neurological examination will be recorded by the investigator in the primary medical documentation and CRF as AEs.

**Vital signs:**

During the Screening visit and Visits 1, 3, 6, and 7, the investigator shall measure the following vital signs: SBP, DBP, heart rate. Clinically significant deviations of vital signs will be recorded by the investigator in the source medical documentation and CRF as AEs.

**Laboratory investigations:**

Blood and urine samples of a study subject will be collected during the Screening visit and Visits 3 and 7 for laboratory safety studies. Valid certificates of laboratories conducting laboratory tests and their norms are included in the study archive. The investigator is responsible for evaluation of all laboratory investigation results of the study subjects, as well as evaluation of clinical significance of any deviations of laboratory parameters. Clinically significant deviations of laboratory analyses results are recorded by the investigator in the primary medical documentation and CRF as AEs.

Laboratory investigation parameters for treatment safety evaluation are presented in Table.

**Table 3. Laboratory investigation parameters for treatment safety evaluation.**

Laboratory investigation	Visits	Parameters
Complete blood count	Screening, Visits 3 and 7	hemoglobin, RBC, hematocrit, PLT, WBC and WBC differential (neutrophils, lymphocytes, monocytes, eosinophils, basophils), ESR
Blood chemistry	Screening, Visits 3 and 7	glucose, urea, creatinine, total bilirubin, total protein, ALT, AST, AP
Urinalysis	Screening, Visits 3 and 7	relative density, protein, sugar, RBC, WBC

Strictly confidential. Proprietary Information.  
[name]

**Table 3. Laboratory investigation parameters for treatment safety evaluation (continued).**

Laboratory investigation	Visits	Parameters
Infection blood test	Screening	RW blood test, HBV, HCV, HIV infection tests
Determination of blood immunoglobulin levels	Visits 1 and 7	Immunoglobulin E (IgE)

**Assessment of local and systemic reactions to vaccine administration (reactogenicity)**

For assessment of local and systemic reactions to vaccine administration, the results of daily examinations are recorded in a Case Report Form and an Outpatient Medical Record for each subject. Particular attention is paid to symptoms corresponding to clinical manifestations of influenza, allergic and neurological reactions. A local reaction is evaluated by the diameter of a hyperaemic skin area at the injection site, skin tenderness and oedema, and enlargement of regional lymph nodes.

The assessment is performed before immunization, 2 hours after immunization, then once a day for 5 post-immunization days; thermometry is mandatory. Subjects who responded to the vaccination are monitored until these reactions pass off completely. In case of development of any unusual reactions the subject will be examined by an appropriate specialist. The following parameters are used for evaluation of tolerability of the study drugs.

***Local reactions:***

1. Pain at the injection site
2. Redness (mm)
3. Swelling, induration (mm)
4. Infiltrate (mm)
5. Itch
6. Enlargement of regional lymph nodes

***Systemic reactions:***

1. Increase of body temperature over 37 °C
2. Malaise
3. Headache
4. Sleep disturbance
5. Appetite disturbance
6. Nausea
7. Vomiting
8. Abdominal pains
9. Stuffy nose

---

Strictly confidential. Proprietary Information.  
[name]

10. Cough
11. Pharynx hyperaemic
12. Increased sweating
13. Tremor
14. Myalgia, arthralgia.

The nature and duration of immunization reactions in vaccinated subjects is compared upon interpretation of all study materials. An analysis of this data will make it possible to formulate a conclusion and resolve the issue of tolerability of study vaccines.

The course of the post-immunization period is assessed as smooth or complicated. Complicated course of the post-immunization period is considered as integration of intercurrent diseases after immunization. The absence of intercurrent diseases is considered as smooth post-immunization period. Fever responses were classified by temperature increase as follows: mild (low-grade fever up to 37.5 °C), moderate (temperature rise from 37.6 °C to 38.5 °C), and severe (temperature rise above 38.6 °C).

Local immunization reactions are classified as mild, moderate, and severe. Erythema without infiltration up to 50.0 mm in diameter at the injection site or infiltration up to 25.0 mm in diameter is estimated as a mild local reaction; erythema with a diameter more than 50.0 mm or an infiltrate with a diameter 26.0 to 50.0 mm was estimated as a moderate local reaction; infiltration more than 50.0 mm in diameter was estimated as a severe local reaction (Methodological Guidelines MU 3.3.2.1758-03 "Methods for determination of quality indicators of immunobiological products for prevention and diagnostics of influenza"). When the reaction is free of redness and/or infiltration, the reaction severity is accepted as indeterminate.

Local reactions will be assessed in all subjects, since local reactions were directly related to the administration of the vaccine.

Occurrence of general symptoms on the first 3 days after (and even on the day of immunization) may be associated with immunization (systemic reactions). However, it does not rule out their causal relationship with diseases, accidentally occurring within the first days of post-immunization period.

According to the accepted methods of interpretation of the vaccinal process course, assessment of general reactions will only be performed in volunteers with a smooth course of vaccinal process, because in a complicated course of post-immunization process, the observed symptoms may be associated with an intercurrent disease rather than with immunization. Thus, in case of development of an infectious intercurrent disease, including ARD/ARI in a volunteer within the first days after immunization, the general symptoms observed should be excluded from systemic reactions recorded within the first 5 days.

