#### **4.2. Subject non-inclusion criteria**

*Specific:*

1. Contraindications listed in the protocol and prescribing information for inactivated influenza vaccines:
  - acute infections and non-communicable disorders, including the period of convalescence of at least one month from the time of clinical and laboratory evidence of recovery;
  - hepatitis or meningococcal infection occurred less than 6 months after recovery;
  - exacerbations of chronic disorder or decompensated disorders that may impact the study (organic central nervous system disorders, decompensated cardiovascular disorder, acute renal or hepatic failure);
  - malignant neoplasms (including hematological disorders);
  - primary immunodeficiency (laboratory-confirmed);
  - HIV infection or HIV-associated disorders;
  - systemic disorders of connective tissue;
  - haemophilia (and other blood coagulation disorders);
  - severe neurological disorders;
  - Guillain–Barré syndrome (post infection demyelinating polyradiculoneuropathy of autoimmune nature with peripheral limb muscle palsy related to inflammation and destruction of myelin sheath of peripheral nerves; may acquire an ascending nature, involving muscles of face, pharynx, larynx);
  - history of severe vaccine-associated reactions (body temperature exceeding 38.5 °C) or local reactions (hyperemia and/or oedema at the site of injection of over 5 cm in diameter);
  - history of severe allergic disorders (angioedema, polymorphic exudative erythema, serum disease, etc.);
  - hypersensitivity to chicken protein or vaccine components;
  - blood and components transfusion within the last 6 months.
2. Indications for immunomodulating therapy.
3. Body temperature over 37.0 °C at screening or before injection.
4. Potential evidence of a chronic infection (periodic episodes of fever within the last 6 months), or antiviral (and/or antibacterial) treatment indicated.
5. History of disorders or conditions, which, according to investigator's judgment may impact the thermal regulation (chronic infections, neuroendocrine disorders [thyrotoxicosis, pheochromocytoma, etc.], climacteric syndrome, malignant hyperthermia, CNS disorders,

---

Strictly confidential. Proprietary Information.  
[name]

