#### **7.3.1.1. Evaluation of severity of adverse event**

The investigator should assess the severity of each AE using the following AE severity classification:

- mild: with or without symptoms, which are easily tolerated without treatment;
- moderate: minimum or local non-surgical treatment is indicated, may interfere with daily activities;
- severe: may interfere with daily activities, may require hospitalization or extension of existing hospitalization.

If severity of the AE changed in the course of its development, maximum severity should be reported.

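### The Section 7.2 fever scale leaves 38.6 °C ungraded, and a fever also recorded as an AE is graded again under Section 7.3.1.1 with no rule linking the two scales

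*Combined protocol and SAP*

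**What the plan says.** Section 7.2 (Systemic reactions) lists a temperature reaction as "Increase of body temperature over 37 °C" and grades it mild up to 37.5 °C, then "moderate (temperature rise from 37.6 °C to 38.5 °C), and severe (temperature rise above 38.6 °C"). Temperature is the only one of the 14 listed systemic items that receives a numeric grade there.

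Section 4.2, repeated in the Synopsis, excludes volunteers with a "history of severe vaccine-associated reactions (body temperature exceeding 38.5 °C").

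Section 7.3.1.1 has its own scale and exempts nothing: "The investigator should assess the severity of each AE using the following AE severity classification". Its lowest grade is "mild: with or without symptoms, which are easily tolerated without treatment". Moderate applies where limited or local non-surgical treatment is called for, and it carries a clause on interference with daily activities. The top grade is "severe: may interfere with daily activities, may require hospitalization or extension of existing hospitalization", so it repeats that clause.

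Section 7.2 sends clinically significant complaints from the interview and the diary into the CRF as AEs. Section 8.1 (Safety analysis) tabulates AEs by severity and separately promises: "The number (percentage) of volunteers with local and general reactions to vaccination will be presented taking into account severity and duration". Section 3.6 makes a severe AE a ground for excluding a volunteer. Section 8.5 requires members of the per-protocol set to have completed the study.

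**The concern.** Severity of local and systemic reactions is a listed safety parameter (Section 3.1), so each reaction that the plan grades should receive exactly one grade on a stated scale. Three features work against that. One temperature falls between two bands. A fever reaction that becomes an AE falls under two scales built on different criteria, with no precedence or mapping rule. One of the criteria in the AE scale is common to moderate and severe.

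If this is left alone, the reaction table and the AE table may show different severities for the same event, and a reader could not tell why. Severe AE also triggers exclusion. Uncertainty about which scale defines it can therefore decide who is withdrawn, and so who remains in the per-protocol set.

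**Working it through.** The plan states no figure to reproduce on this point. The check applies the rules as written.

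**1. Coverage of the fever bands.** Inputs are the Section 7.2 bands and the lower limit of over 37 °C. I assume readings are recorded to 0.1 °C, the resolution at which the bands are written. Going through 37.1 to 41.0 °C gives 40 readings:

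| Band as written | Readings | Count |
|---|---|---|
| Mild: over 37 up to 37.5 | 37.1–37.5 | 5 |
| Moderate: 37.6 to 38.5 | 37.6–38.5 | 10 |
| No band | 38.6 | 1 |
| Severe: above 38.6 | 38.7–41.0 | 24 |

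5 + 10 + 1 + 24 = 40. Exactly one reading has no grade, and none has two.

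**2. Agreement with Section 4.2.** Under the entry criterion, 38.6 > 38.5, so a past reaction of 38.6 °C counts as severe. Under Section 7.2, 38.6 is not above 38.6, so the same temperature after study vaccination is not severe, and it is not moderate either.

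**3. One event on both scales.** Take a fever of 38.8 °C, easily tolerated and untreated, that the investigator records as an AE.
- Section 7.2: 38.8 > 38.6, so severe.
- Section 7.3.1.1: easily tolerated without treatment, so mild.

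The grades are two steps apart. The example avoids the moderate/severe line in 7.3.1.1, so it does not depend on how that line is read.

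**4. Whether the overlap arises in practice.** Section 1.2 reports that most Phase I AEs were classed as post-immunization reactions, and Table 1 in Section 1.3 lists raised body temperature as an AE. Fever is therefore expected in both tables.

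**5. Moderate against severe in Section 7.3.1.1.**

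| Criterion | Moderate | Severe |
|---|---|---|
| Daily activities | may be affected | may be affected |
| Treatment | limited or local, non-surgical | not stated |
| Hospitalization | not stated | may be needed |

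The first row does not discriminate. The other two do.

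**6. Size.** The plan gives no rate for fever of 38.6 °C or above. In Phase I (Section 1.2), 6.9 % on Grippol Quadri (2/29) had a temperature reaction, with a maximum of 37.2 °C. The placebo maximum was 37.5 °C. These data cannot support an expected count of discordant grades.

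**The case against.** The strongest reply is that each scale has its own scope. Section 7.2 grades reactions and Section 7.3.1.1 grades AEs, and severe AE in Section 3.6 is most naturally read on the AE scale. The boundary at 38.6 °C looks like a slip for a band starting at that value. On that reading both the gap and the mismatch with Section 4.2 disappear. Moreover, Section 4.2 is an entry criterion, not an outcome scale, and no Phase I temperature reaction came near the boundary. These are fair reasons to rate the point as modest. They do not supply the missing rule: the text as written has a gap, and nothing says how a reaction recorded as an AE is graded.

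Two stronger readings are tempting, and the documents do not support them.
- **That the severe counts in the two tables contradict each other.** The plan contains no counts, and the tables differ in scope. General reactions are assessed only in volunteers with a smooth post-vaccination course (Section 7.2), while AEs are tabulated for everyone dosed. Counts can differ legitimately. Phase I already shows 2/29 with fever as a general reaction and 3/30 with raised temperature as an AE on Grippol Quadri. Most systemic items also have no numeric grade in 7.2 to conflict with.
- **That about 42 of 204 Grippol Quadri volunteers are affected** (204 × 6/29 = 42.2). That figure counts any systemic reactor at the Phase I rate. It does not count high fevers or discordant grades, and all Phase I systemic reactions were mild.

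Nor does 7.3.1.1 fail to separate moderate from severe altogether, because treatment need and possible hospitalization still do so.

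**Conclusion.** The point holds in limited form. Assuming 0.1 °C recording, Section 7.2 leaves one reading, 38.6 °C, without a grade and disagrees with Section 4.2 at that value. A fever reaction that is also an AE can differ by up to two grades between the two scales, and the plan has no rule to reconcile them. The daily-activities criterion does not separate moderate from severe AEs.

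The consequence is for descriptive safety tables. A further route, through exclusion for a severe AE (Section 3.6), could alter membership of the per-protocol set, but the documents do not show how often. The number of affected events cannot be estimated, and Phase I gives no sign that it would be large. The primary endpoint, its method of analysis and the sample size do not use severity grades.

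**What to change.** 1. In Section 7.2, make the fever bands contiguous so that every 0.1 °C reading has exactly one grade, and reconcile the severe boundary with Section 4.2 and the Synopsis.
2. In Section 8.1, name the severity scale used in each safety table. In Section 7.2 or 7.3.1.1, state how a solicited reaction recorded as an AE is graded.
3. In Section 7.3.1.1, remove the daily-activities criterion that moderate and severe share, so that each criterion belongs to one grade.
4. Reconcile Sections 3.6, 7.2 and 7.3.1.1 on which scale severe AE refers to.

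The cut-offs and grade definitions are for the sponsor to choose. The cost is wording in these sections and one CRF instruction, with no new data. It should be done before grading starts. Fever bands can be re-derived later from recorded temperatures, but AE severity is an investigator's judgement made as events occur.
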